10.2.2. Definition of CA-125 Response

CA-125 levels will be drawn at the start of each cycle. A CA-125 response occurs if, after two elevated levels before therapy, a subsequent sample (taken at least 4 weeks +/- 1 week after initiating cediranib/olaparib) shows at least a 50% decrease that is confirmed by a sequential confirmatory sample (taken 4 weeks +/- 1 week after the prior sample). The confirmatory sample must be less than or equal to 110% of the prior sample showing a response.

10.2.3. Definition of CA-125 progression:

No validated definitions of CA-125 progression have been published to date. Given the potential cytostatic nature of angiogenesis inhibitors such as cediranib, in this trial the criterion for progression based on CA-125 level is: **doubling of the CA-125 level from BASELINE (pre-treatment).**

As long as interval CA-125 measurements are less than double the value from baseline, subjects may continue on study, provided that tumor measurements are stable as well, without the development of new lesions.

10.3. Response Criteria

Clinical response benefit is defined as:

- a) For patients with only an elevated CA125 (no measurable cancer via radiographic test): Modified GCIG CA-125 response (see Section 10.2) without progressive disease on CT scan for at least 16 weeks

OR

- b) For patients with measurable disease: Tumor response by RECIST criteria or stable disease for at least 16 weeks.

10.4. Confirmatory Measurement/Duration of Response

10.4.1. Confirmation

To be assigned a status of clinical response benefit, the modified GCIG CA-125 response criteria incorporate the need for a sequential confirmatory CA-125 level as described in Section 10.2.

For patients being followed with measurable disease, changes in tumor measurements must be confirmed by repeat assessments that should be performed at least 4 weeks after the criteria for response are met. The next scheduled CT or MRI may be used as the confirmatory scan. In the case of SD, follow-up measurements must have met the SD criteria for at least 16 weeks, with scans every 8 weeks (+/- 1 week).

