- j: ECG done prior to Cycle 1 and 2, and then prior to every cycle if clinically indicated. The pre-study ECG may be used as the Cycle 1 ECG if performed within 7 days of Cycle 1 Day 1.
- k: MUGA or echocardiogram should be done at baseline and every 4 cycles for those patients at increased risk for compromised LVEF. Increased risk patients have had one or more of the following: (1) prior treatment with anthracyclines, (2) prior treatment with trastuzumab, (3) NY Heart Association classification of II, (4) prior central thoracic RT, (5) history of myocardial infarction within the 12 months prior.
- l: beta-HCG for women of childbearing potential.
- m: Tumor measurements by CT scans or MRI will be performed within the 4 weeks prior to starting cediranib/olaparib and will be performed after every 8 weeks (+/- 1 week) of treatment. If a partial or complete response is noted, a confirmatory CT scan or MRI should be performed. The next planned restaging CT scan or MRI may be used as the confirmatory scan. For patients in the Phase 2 portion of the trial, the frequency of restaging studies will decrease to once every 12 weeks (+/- 1 week) after the 20th cycle of treatment.
- n: The Family Risk Assessment questionnaire (Appendix I) should be completed by the patient and returned to the study staff by Cycle 2.
- o: For patients opting to participate in translational studies at the NCI. Study schedules will be as per Section 5.1.4.
- p: Off-treatment assessments should be performed within 30 days of stopping study treatment.
- q: For patients in the Phase 2 portion of the trial who have been on trial for greater than 4 years without evidence of disease progression, the treating investigator may choose to decrease the frequency of re-staging CT scans to once every 4 cycles.
- r: For patients in the Phase 2 portion of the trial who have been on trial for greater than 4 years without evidence of disease progression, the treating investigator may choose to decrease the frequency of visits to once every 2 cycles. These patients should have CBC with differential, serum chemistry, and urine protein assessment (UPC or urinalysis) performed and con-meds, adverse events, and blood pressure diary should be reviewed in-person or by telephone with the study team, but all other assessments may be omitted.

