10.4.3. Duration of Stable Disease

Stable disease is measured from the start of the treatment until the criteria for progression are met, taking as reference the smallest measurements recorded since the treatment start, with stable disease of at least 16 weeks meeting the primary objective of the Phase II component.

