10.4.4. Duration of Response

Duration of overall response: The duration of overall response is measured from the time measurement criteria are met for CR or PR (whichever is first recorded) until the first date that recurrence or PD is objectively documented, taking as reference for PD the smallest measurements recorded since the treatment started.

Duration of overall complete response: The duration of overall CR is measured from the time measurement criteria are first met for CR until the first date that recurrent disease is objectively documented.

Duration of stable disease: Stable disease is measured from the start of the treatment until the criteria for progression are met, taking as reference the smallest measurements recorded since the treatment started.

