14.1.2. Secondary Objectives

1. **Phase 1 Component:** Assess the toxicities of the combination of cediranib and olaparib in the treatment of recurrent ovarian, fallopian tube, and peritoneal cancer or metastatic triple-negative breast cancer
2. **Phase 2 Component:** Investigate tumor response rate, clinical benefit rate (response or stable disease x 16 weeks, as determined by RECIST 1.1 criteria, and overall survival for patients with recurrent platinum-sensitive grade 2 or 3 papillary-serous or endometrioid ovarian, fallopian tube, or peritoneal cancer treated with cediranib and olaparib at the RP2D compared to cediranib alone.
3. **Phase 1-T (tablet) Component:** Assess the toxicities of the combination of cediranib and olaparib in the treatment of recurrent ovarian, fallopian tube, and peritoneal cancer.

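### Clinical benefit has two conflicting 16-week stable-disease rules (10.4.1 and 10.4.3), and the threshold falls inside the week 15–17 window for the second scan

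*Combined protocol and SAP*

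**What the plan says.** Section 14.1.2 makes the "clinical benefit rate (response or stable disease x 16 weeks, as determined by RECIST 1.1 criteria") a Phase II secondary objective, and 14.2 includes it in the power statement for the comparison of rates. For measurable disease, which every Phase II patient must have, section 10.3 defines benefit as "Tumor response by RECIST criteria or stable disease for at least 16 weeks".

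The timing comes from section 9.2, footnote m. Scans "will be performed after every 8 weeks (+/- 1 week) of treatment", so scan 1 falls in weeks 7–9, scan 2 in weeks 15–17 and scan 3 in weeks 23–25. The baseline scan may be up to 4 weeks old: "Tumor measurements by CT scans or MRI will be performed within the 4 weeks prior to starting cediranib/olaparib".

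Three sections then say how SD is timed:

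- **10.4.1** sets a condition on the scans: "follow-up measurements must have met the SD criteria for at least 16 weeks, with scans every 8 weeks (+/- 1 week"). It gives no start point for the 16 weeks.
- **10.4.3** times SD from treatment start to the date on which progression criteria are met, and ties the threshold to that duration, "with stable disease of at least 16 weeks meeting the primary objective of the Phase II component".
- **10.4.4** repeats the duration rule without a threshold: "Stable disease is measured from the start of the treatment until the criteria for progression are met".

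Nothing says which rule governs, and the 16 weeks carry no tolerance to match the scan window.

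**The concern.** Sections 10.4.1 and 10.4.3 ask different questions. The first asks how late the last scan showing SD was. The second asks how late the scan showing progression was. With scans 8 weeks apart, the answers can differ by a whole interval.

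Because the threshold sits at the nominal date of scan 2, that gap decides cases. A patient whose week-16 restaging shows progression can be counted as benefiting. A patient who is stable at a restaging done within the allowed window can be counted as not benefiting. The rate in each arm and the difference between arms then depend on which section the analyst follows, and partly on the day of the scan. If the rule is chosen after the data are in, it can be chosen with the results in view.

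**Working it through.** **The plan's own figure.** The only number given for this endpoint is 80% power for 20% against 49.5% with 41 per arm at alpha 0.05 (14.2). The two-sided normal approximation with mean rate 0.3475 gives z = [0.295·√41 − 1.96·√(2·0.3475·0.6525)] / √(0.20·0.80 + 0.495·0.505) = (1.889 − 1.320)/0.640 = 0.889, a power of 81%. The figure reproduces. It uses response rates, however, and says nothing about how SD is timed.

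**The rules applied to individual patients.** Here 10.4.1 is read as time from treatment start to the last SD scan.

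| Scan 1 | Scan 2 | Scan 3 | 10.4.1 | 10.4.3 |
|---|---|---|---|---|
| SD | PD, week 16–17 | – | last SD week 7–9: no | 16–17 weeks: yes |
| SD | PD, before week 16 | – | no | under 16 weeks: no |
| SD | SD, before week 16 | PD | under 16 weeks: no | 23–25 weeks: yes |
| SD | SD, week 16–17 | PD | yes | yes |
| SD | SD, any compliant day | SD | yes | yes |

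The rules part in the first and third rows, and in both 10.4.3 is the more generous.

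**Size.** Inputs are the median PFS values of 6 and 10.5 months from 14.2. Assumptions are exponential progression times, progression detected at the next scan, and no responders. S(t) = 2^(−t/m), with m = 6 × 4.348 = 26.09 weeks for control and 10.5 × 4.348 = 45.66 weeks for the combination.

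- S(8) = 0.8085 and 0.8856; S(16) = 0.6537 and 0.7843 (control, combination).
- Scans on time: 10.4.1 gives S(16). 10.4.3 gives S(8), because progression first seen at week 16 still counts. The gap is S(8) − S(16) = 0.155 and 0.101.
- Scans all one week early: 10.4.1 gives S(23) and 10.4.3 gives S(15). All one week late: S(17) and S(9).
- Scans uniform within ±1 week: simulation of 2 million progression times.

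Percentages are control / combination. Differences come from unrounded values.

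| Scan timing | 10.4.1 (difference) | 10.4.3 (difference) | Rules disagree |
|---|---|---|---|
| On time | 65.4 / 78.4 (13.1) | 80.9 / 88.6 (7.7) | 15.5 / 10.1 |
| Uniform in window | 58.7 / 73.7 (15.0) | 73.6 / 83.9 (10.3) | 14.9 / 10.2 |
| All 1 week early | 54.3 / 70.5 (16.2) | 67.1 / 79.6 (12.5) | 12.9 / 9.1 |
| All 1 week late | 63.7 / 77.3 (13.6) | 78.7 / 87.2 (8.5) | 15.1 / 10.0 |

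Of 41 patients per arm, that is about 6 in control (41 × 0.155 = 6.4) and 4 in the combination arm (41 × 0.101 = 4.1).

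**The same data classified by status at scan 2.** Counting patients without progression at scan 2, whatever its day in the window, gives 65.4 / 78.4 on time, 65.4 / 78.5 uniform, 67.1 / 79.6 early and 63.7 / 77.3 late. The between-arm difference stays between 12.5 and 13.6 points. Over the same timings the control rate runs from 54.3% to 65.4% under 10.4.1 and from 67.1% to 80.9% under 10.4.3.

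**The case against.** The best defence is that the sections do different jobs: 10.4.1 sets the qualifying condition and 10.4.4 only describes duration. A scan showing progression does not meet SD criteria, so SD at week 8 with progression at week 16 fails. For 10.4.4, which has no threshold, this is a fair reading. It does not dispose of 10.4.3, which attaches the 16 weeks to the time from start to progression, and the text gives no order of precedence.

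A second defence concerns patients stable at an early scan 2. The sentence in 10.4.1 that sets 16 weeks also states the ±1 week window, so two in-window SD scans might be meant to satisfy it. It names no start point, and counting from a baseline scan taken before treatment could bring a week-15 scan up to 16 weeks. This stands in part: the exclusion is possible, not certain, and a patient still stable at scan 3 qualifies under both rules. The open start point is itself something to settle.

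A reader might infer that restaging before cycle 5 will often miss the threshold, since four cycles end on day 112. The documents give no distribution of scan days, and with on-time or late scans no patient is lost this way.

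The size also needs restraint. Responders count as benefit under either rule, and the plan's alternative has 49.5% responders in the combination arm. The change in the between-arm difference, about 5 points on time or uniform (13.1 − 7.7 = 5.4; 15.0 − 10.3 = 4.7), is smaller than its standard error of about 10 points: √[(0.653·0.347 + 0.784·0.216)/41] = 0.098.

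**Conclusion.** The conflict is real and lies in current text. SD at scan 1 with progression at scan 2 on or after week 16 is benefit under 10.4.3 and not under 10.4.1. A patient stable at a compliant scan 2 before week 16 who then progresses at scan 3 can fail 10.4.1 if the 16 weeks run from treatment start.

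Under the assumed curves, the rules disagree for up to about 15 points in control and 10 in the combination arm. These are upper bounds for each arm because responders are left out. The between-arm differences illustrate the no-responder case and are not bounds, since the arms may differ in their share of responders. It would go too far to say that the reported rates will be wrong by 10 to 15 points.

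A reader might also take 10.4.3 to put the primary analysis in doubt, because it calls 16-week SD the Phase II primary objective. Sections 1.2.2 and 14.1.4 name PFS, and neither the PFS analysis nor the objective response rate uses the 16-week rule. This is a correction that should be made to one secondary endpoint.

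**What to change.** Define SD for clinical benefit by assessment in 10.3, 10.4.1 and 10.4.3, and use the same definition in 1.3.2, 14.1.2 and 14.1.5:

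- No progression at the first restaging, and SD or better at the second scheduled restaging (nominal week 16, window weeks 15–17).
- If the second restaging is late or missed, SD or better at the next scan.
- Progression found at the second restaging is not clinical benefit, whatever its date.

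Keep the start-to-progression rule in 10.4.3 and 10.4.4 only to describe how long SD lasted. Delete from 10.4.3 the statement that 16-week SD meets the Phase II primary objective.

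The cost is wording in six sections, with no extra scans or patients. The reported benefit rate may be somewhat lower than under 10.4.3, because progression at the week-16 restaging would no longer count.

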10.4.2. Duration of Overall Response

The duration of modified GCIG CA-125 response or RECIST assessment is measured from the time measurement criteria are met (see Section 10.1) until the first date that recurrent or progressive disease is objectively documented by CA-125 level (taking as reference for progression of CA-125 the baseline measurement of CA-125 recorded pretreatment) or by progressive disease noted on CT scan by RECIST criteria.

10.4.3. Duration of Stable Disease

Stable disease is measured from the start of the treatment until the criteria for progression are met, taking as reference the smallest measurements recorded since the treatment start, with stable disease of at least 16 weeks meeting the primary objective of the Phase II component.

10.4.4. Duration of Response

Duration of overall response: The duration of overall response is measured from the time measurement criteria are met for CR or PR (whichever is first recorded) until the first date that recurrence or PD is objectively documented, taking as reference for PD the smallest measurements recorded since the treatment started.

Duration of overall complete response: The duration of overall CR is measured from the time measurement criteria are first met for CR until the first date that recurrent disease is objectively documented.

Duration of stable disease: Stable disease is measured from the start of the treatment until the criteria for progression are met, taking as reference the smallest measurements recorded since the treatment started.

10.4.5. Progression-Free Survival

Progression-Free Survival (PFS) is defined as the duration of time from start of treatment to time of objective disease progression.

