5.6. Duration of Follow Up

Participants will be followed for 3 years after removal from study treatment or until death, whichever occurs first. Participants removed from study treatment for unacceptable adverse events will be followed until resolution or stabilization of the adverse event. Participants' vital status will be followed every 6 months following removal from the study treatment. Date and cause of death should be provided for participants who become deceased within the 3 year interval following removal from the study treatment.

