10.1.1. Definitions

Evaluable for toxicity. All participants who receive at least one dose of study treatment will be evaluable for toxicity from the time of their first treatment with cediranib and olaparib.

Evaluable for objective response. Only those participants who have measurable disease present at baseline, have received at least one cycle of therapy, and have had their disease re-evaluated will be considered evaluable for response. These participants will have their response classified according to the definitions stated below. (Note: Participants who exhibit objective disease progression or die prior to the end of cycle 1 will also be considered evaluable.)

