¹ Adverse events with attribution of possible, probable, or definite that occur greater than 30 days after the last dose of treatment with an agent under a CTEP IND require reporting as follows: CTEP-AERS 24-hour notification followed by complete report within 5 calendar days for: 
 • Grade 4 and Grade 5 unexpected events CTEP-AERS 10 calendar day report: 
 • Grade 3 unexpected events with hospitalization or prolongation of hospitalization • Grade 5 expected events ² Although an CTEP-AERS 24-hour notification is not required for death clearly related to progressive disease, a full report is required as outlined in the table.									
December 15, 2004									

Note: All deaths on study require both routine and expedited reporting regardless of causality. Attribution to treatment or other cause must be provided.

- Expedited AE reporting timelines defined:
 - “24 hours; 5 calendar days” – The investigator must initially report the AE via CTEP-AERS within 24 hours of learning of the event followed by a complete CTEP-AERS report within 5 calendar days of the initial 24-hour report.

- “10 calendar days” - A complete CTEP-AERS report on the AE must be submitted within 10 calendar days of the investigator learning of the event.
- Any medical event equivalent to CTCAE grade 3, 4, or 5 that precipitates hospitalization (or prolongation of existing hospitalization) must be reported regardless of attribution and designation as expected or unexpected with the exception of any events identified as protocol-specific expedited adverse event reporting exclusions.
- Any event that results in persistent or significant disabilities/incapacities, congenital anomalies, or birth defects must be reported via CTEP-AERS if the event occurs following treatment with an agent under a CTEP IND.
- Use the NCI protocol number and the protocol-specific patient ID assigned during trial registration on all reports.

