The expected PFS to a platinum-based regimen in this setting is approximately 6 months (Markman *et al.*, 1991). The PFS observed with cediranib alone in this patient population was 5.2 months (Matulonis *et al.*, 2009). In the Phase II study of olaparib in BRCA mutation carriers, the estimated PFS ranged from approximately 2.5 months to 5.5 months between the 100mg BID and 400mg BID cohorts (Audeh *et al.*, 2010). In BRCA wild-type patients, the estimated response rate was 23.9% (Gelmon *et al.*, 2010), which is comparable to the 20% response rate observed with single-agent cediranib (Matulonis *et al.*, 2008). Given this similar activity and the observed data in the Audeh *et al.* Phase II trial, we therefore project a PFS in a control arm of olaparib alone to be similar to that of platinum-based regimens at 6 months. An increase in progression-free survival to 10.5 months (from the projected 6 months) would be considered of clinical interest. In the Phase II portion of the study, for a power of 86% to reject H_0 : Median PFS in both arms = 6 months in favor of H_1 : Median PFS of the group with olaparib combination > 10.5 months with an alpha of 0.10, 71 events (i.e., disease progressions) out of a total of 82 evaluable patients will be required to detect a hazard ratio of 0.5716 (experimental over control). We will therefore perform the final PFS analysis when the 71st evaluable patient experiences cancer progression. It is anticipated that 10% of subjects will not be evaluable, and thus the total number of subjects with platinum-sensitive disease to be enrolled in the Phase II portion of the study is 90. Progression-free survival will be evaluated by Kaplan-Meier analysis and Log-Rank test for between group comparison, and median survival times reported. To minimize the likelihood of exposing study patients to an inactive regimen, an interim assessment of the hazard ratio for disease progression (experimental over control) will be performed when the 36th patient experiences cancer progression. If the estimated hazard ratio at that time is 1 or greater, accrual to the study will be halted for futility.

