14.3.2. Evaluation of Response

All patients included in the study must be assessed for response to treatment, even if there are major protocol treatment deviations or if they are ineligible. Each patient will be assigned one of the following categories: 1) complete response, 2) partial response, 3) stable disease, 4) progressive disease, 5) early death from malignant disease, 6) early death from toxicity, 7) early death because of other cause, or 9) unknown (not assessable, insufficient data). By arbitrary convention, category 9 usually designates the "unknown" status of any type of data in a clinical database.

All of the participants who met the eligibility criteria (with the possible exception of those who received no study medication) should be included in the main analysis of the response rate. Participants in response categories 4-9 should be considered to have a treatment failure (disease progression). Thus, an incorrect treatment schedule or drug administration does not result in exclusion from the analysis of the response rate. Precise definitions for categories 4-9, and sometimes category 3, will be protocol specific.

All conclusions should be based on all eligible participants. Subanalyses may then be performed on the basis of a subset of participants, excluding those for whom major protocol deviations have been identified (e.g., early death due to other reasons, early discontinuation of treatment, major protocol violations, etc.). However, these subanalyses may not serve as the basis for drawing conclusions concerning treatment efficacy, and the reasons for excluding participants from the analysis should be clearly reported. The 95% confidence intervals should also be provided.

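### The Phase II primary endpoint is named PFS but is defined and counted by progression alone, so followed literally it is time to progression

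*Combined protocol and SAP*

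**What the plan says.** Sections 1.2.2, 14.1.1 and 14.1.4 name PFS as the Phase II primary objective or endpoint and add no event rule. The only definition is in section 10.4.5: "Progression-Free Survival (PFS) is defined as the duration of time from start of treatment to time of objective disease progression". Death is not mentioned.

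Section 14.2 uses the same event throughout. On size, it says "71 events (i.e., disease progressions) out of a total of 82 evaluable patients will be required". On timing, "We will therefore perform the final PFS analysis when the 71st evaluable patient experiences cancer progression". For futility it plans "an interim assessment of the hazard ratio for disease progression (experimental over control) will be performed when the 36th patient experiences cancer progression", and accrual stops if that hazard ratio is 1 or more. No censoring rule for the primary analysis is given.

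Two passages mention death near efficacy. Section 14.3.2 lists early death (from malignant disease, toxicity or another cause) among the response categories and says "Participants in response categories 4-9 should be considered to have a treatment failure (disease progression"). The note in section 10.1.1 says "Participants who exhibit objective disease progression or die prior to the end of cycle 1 will also be considered evaluable". Both concern response.

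**The concern.** PFS is ordinarily read as time to progression or death. Here the definition, both triggers and the futility statistic all leave death out. A result reported as PFS would therefore measure something narrower, and a difference between arms in deaths without progression would not enter the primary log-rank test or the futility decision.

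Such a difference is plausible, though not established. Only the combination arm receives cediranib. Section 2.2.1 reports that some gastrointestinal perforations with it were fatal, and section 6.1.1 lists perforation among rare but serious events (under 3%). Against that, section 2.1.2 describes a cediranib study in ovarian cancer with no perforations.

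The progression-only trigger can also fail. If exactly 82 patients are evaluable, at most 82 − 71 = 11 may lack documented progression before the 71st progression becomes unreachable. If all 90 are evaluable, the limit is 90 − 71 = 19.

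**Working it through.** **Does any passage add death to the endpoint?** Section 14.3.2 comes closest, because it equates early death with disease progression, the term section 14.2 uses for its events. But it sits under evaluation of response and governs the response-rate analysis. It covers only early deaths, and it also includes the unknown category, so as a PFS rule it would turn missing data into progressions. Section 10.1.1 decides who is evaluable for objective response. Neither sets a PFS event or date.

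**The plan's own figure.** Inputs from section 14.2: 71 events, hazard ratio 0.5716, alpha 0.10; 1:1 allocation from section 5. Schoenfeld power = Φ(½ × √71 × |ln 0.5716| − z). Here ½ × √71 = 4.213 and |ln 0.5716| = 0.5593, with product 2.356. One-sided, z = 1.282 gives Φ(1.075) = 85.9%, the stated 86%. Two-sided, z = 1.645 gives 76.2%. The design therefore reproduces as one-sided 0.10. The formula does not depend on which event is counted, so 71 stands if 0.5716 is the target for progression or death.

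**If 0.5716 applies to progression alone.** Let f be the share of control first events that are deaths without progression (assumed), with equal death hazards in the two arms. The composite hazard ratio is 0.5716 × (1 − f) + f. For f = 0.10 this is 0.514 + 0.100 = 0.614, and power at 71 events is Φ(4.213 × 0.487 − 1.282) = 78%. Events needed for 85.9% power are 4 × 2.356² / (ln HR)².

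**Reaching 71 progressions.** The chance that a first event is a progression is 1 − f on control and 0.5716(1 − f) / [0.5716(1 − f) + f] on the combination. For f = 0.10 these are 0.900 and 0.837, so 82 patients yield on average 41 × 1.737 = 71.2 progressions, barely the number required. The last two columns come from simulation (20,000 runs per row) and assume no other loss to follow-up.

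| Assumed f | Composite HR | Power at 71 events | Events for 85.9% | 71 progressions never reached, 90 patients | Same, 82 patients |
|---|---|---|---|---|---|
| 5% | 0.593 | 82% | 82 | 0% | 1% |
| 10% | 0.614 | 78% | 94 | 1% | 39% |
| 15% | 0.636 | 73% | 109 | 28% | 89% |

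**What the primary test would miss.** A second simulation assumed no effect on progression and 1, 2 or 4 expected deaths in the first 3 months, on the combination arm only (90 patients, 18-month accrual, control median 6 months).

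- Deaths censored: hazard ratio 1.00, about 10% positive tests, about 50% futility stops.
- Deaths counted: hazard ratio 1.03, 1.06 or 1.13; positive tests 8%, 6% or 4%; futility stops 55%, 59% or 69%.

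The death counts are illustrations, and censoring is one reading of the text for early deaths.

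**The case against.** The strongest defence is that the handling of deaths is unstated rather than wrong. Section 14.3.2 could lead an analyst to count an early death as progression, and censoring is nowhere written. That stands in part: for early deaths two analysts could differ. It does not rescue the definition, which is explicit and repeated in section 14.2, and it says nothing about later deaths.

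The effect may also be small. Entry requires ECOG 0 or 1 and life expectancy over 6 months (sections 3.1.5 and 3.1.6), and every death rate above is assumed. This stands, and no size can be claimed.

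Some stronger readings are tempting but unsupported:

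- A reader might infer that the progression-only test inflates type I error. With deaths censored in the null simulation, positive tests stayed at about 10%, the nominal level, for progression.
- A reader might infer that deaths are hidden. They enter overall survival (section 14.2), expedited reporting (section 11.5.1) and monitoring board review (section 12.2).
- A reader might infer that counting deaths guarantees the trigger. It does so only if there is no other loss. With other censoring at an assumed 10% of the control event hazard, and deaths 5% to 15% of control first events, 82 patients still missed 71 events in about 22% to 26% of runs when deaths were counted. Progression alone missed in 80% to 99.9%.

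The note to the best-response table in section 10.1.4 asks sites to try to document progression after treatment stops. That may reduce missing progressions, but it schedules no scans.

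**Conclusion.** The point holds and should be fixed. The event rule as written gives a different endpoint from the one named; this is more than a missing detail. The 71-event arithmetic is sound, and what is wrong is the event it is attached to. The conclusion about the definition rests on the text alone. The bias cannot be sized from the documents, since they give no rate of death without progression. The power and trigger figures hold only under the assumed death shares, equal death hazards and, for the trigger, no other loss to follow-up.

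**What to change.** In section 10.4.5, define Phase II PFS as time to the first of RECIST 1.1 progression or death from any cause. Censor patients without an event at the last adequate tumour assessment. In section 14.2, count both event types toward the 36- and 71-event triggers and in both hazard ratios. State that 0.5716 is the target for progression or death; if it is meant for progression alone, restate the power. Keep time to progression as a sensitivity analysis.

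The 71-event analysis may already have been run: accrual was planned over 18 months, and the section 9.2 footnotes provide for patients on trial beyond 4 years. In that case keep it, label it time to progression, and report progression or death beside it, dated as added later.

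The cost is an amendment to two sections and no new data collection. Section 5.6 already says "Date and cause of death should be provided for participants who become deceased within the 3 year interval following removal from the study treatment", and section 11.5.1 says "All deaths on study require both routine and expedited reporting regardless of causality". The looks would come earlier. Power may fall if treatment acts on progression alone, and restoring it could take more events (94 or 109 at the higher assumed shares) than the 90 patients enrolled. If 1, 2 or 4 expected early deaths fell on the combination arm only, with 0.5716 on progression, simulated power would be 81.5%, 77.5% or 66.6%, and futility stopping 6.8%, 9.3% or 16.2% against 5.0% without such deaths. Patients who stop treatment before progression would still be censored at whatever scan exists.
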